Study Protocol

Predictors of treatment choice in patients with COPD

A retrospective observational cohort study that investigates predictors of initial treatment choice in COPD patients.

Date:

01/02/2014Novartis

Research in Real-Life Pte Ltd
[name]
[name]
Singapore
[name]

Research in Real-Life Ltd
[name]
United Kingdom

Phone [[name]]
Fax ([contact]
Web site <http://www.rirl.org>

Chief Investigator:

[name], Professor of Primary Care Respiratory Medicine and RIRL Director

[contact]

Office number: [name]

Skype ID: [name]

Email: [contact]

Project coordinator:

[name]

Research in Real-Life Ltd

[name]

Direct number: [name]

Email: [contact]

Study sponsor:

Novartis

Primary contact

[name] ([contact])

TITLE	Predictors of treatment choice in patients with COPD
Subtitle	A retrospective observational cohort study that investigates predictors of initial treatment choice in COPD patients.
Protocol version number	V1.0
Medicinal product	N/A
Product code	R04512
Study aims and objectives	
This study aims to examine the changes in prescriptions patterns over time, in order to determine the potential driving factors behind GP prescribing for newly diagnosed COPD patients.
 
The objective of the study is to highlight predictors over time in GP prescription of:
 
 • any initial COPD therapy vs. • no COPD therapy 
and
 
 • maintenance therapy versus • short-acting agents/no therapy
Country of study	United Kingdom
Author	RiRL UK Ltd [name] United Kingdom

Contents

1.0	Background	5
2.0	Study Overview	6
2.1	Study aims & objectives	6
2.2	Study design	6
3.0	Study population	7
3.1	Inclusion and exclusion criteria	7
3.2	Data source	7
4.0	Study variables and study outcomes	8
4.1	Demographic and baseline variables	8
4.2	Primary outcome	8
4.3	Secondary and exploratory outcomes	8
5.0	Statistical analysis	9
5.1	Software used and power calculation	9
5.2	Significance testing	9
5.3	Baseline characterisation	9
5.4	Analysis of study outcomes	9
6.0	Regulatory and ethical compliance	11
7.0	Data dissemination	11
8.0	Advisory group	12
9.0	Research team	12
10.0	Timelines	13
11.0	References	13
12.0	APPENDIX	14
12.1	Appendix 1: Definitions	14
12.2	Appendix 2: Mock baseline results tables	15

1.0 Background

Currently COPD places a high burden on the National Health Service (NHS) in the UK. Current international guidelines for COPD recommend long-acting inhaled bronchodilators, including b2-agonists (LABA) and antimuscarinic agents (LAMA) on a regular basis as monotherapy or in combination with inhaled corticosteroids (ICS) for the symptomatic management of COPD and the prevention of exacerbations. However, it is now widely agreed upon that prescription patterns for Chronic Obstructive Pulmonary Disease (COPD) do not follow international guidelines that are based on randomized clinical trials (RCTs) and more evidence is needed to understand why there is a significant dissociation between guideline recommendations and clinicians' practice.

There is an abundance of literature available from large scale primary care database that provides information on how COPD patients are treated real-life. Indeed a paper recently published by Research in Real Life (RiRL)⁴ gives comprehensive real world findings of how COPD patients are currently being managed with pharmacological therapy. The study reflected that some patients receive no treatment despite experiencing symptoms. Among those on treatment, most received ICS irrespective of severity of airflow limitation, asthma diagnosis, and exacerbation history. Many patients on treatment continued to have symptoms. This highlights the persistent uncertainties of physicians and emphasized that more efforts are required to improve education on and the implementation of COPD guidelines regarding COPD therapies.

Therefore, this study aims to take the work further by exploring the predictors of such prescribing. There may be several reasons for the discrepancy between guidelines and clinical practice including the limited encouragement to implement Guidelines in clinical practice and the individual clinician seeing the Guidelines as an interference to their own clinical judgement. This study will explore in further detail the potential predictors in GP prescribing to determine what could be the driving factors behind GP prescribing to COPD patients (especially in those patients who do not warrant the treatment prescribed).

2.0 Study Overview

2.1 Study aims & objectives

This study aims to examine the changes in prescriptions patterns over time, in order to determine the potential driving factors behind GP prescribing for newly diagnosed COPD patients.

2.2 Study design

A retrospective observational database study using the Optimum Patient Care Research Database. The data utilised in this study ranges from 1997 – 2013. Eligible patients must have a minimum of one year of data prior to their initial date of COPD diagnosis for baseline period, and a minimum of two years of data post their initial COPD diagnosis for outcome period to assess patient characteristics and pharmacological treatment prescriptions.

Cohorts will be chosen to assess how prescription patterns have changed over time and if certain factors such as the introduction of QoF1 in 2004 and Tiotropium (LAMA) becoming licensed in UK in January 2002 influence prescribing behaviour.

Patients will be split into three cohorts based on their date of initial COPD diagnosis:

- 1997 – 2001
- 2002 – 2006
- 2007 – 2010

COPD initial therapy will be defined as pharmacological therapy prescribed during one year prior to and at the initial date of COPD diagnosis (baseline period). COPD therapies will be grouped by treatment class:

- Inhaled corticosteroid (ICS),
- long-acting β_2 -agonist (LABA),
- long-acting muscarinic antagonist (LAMA),
- short-acting β_2 -agonist (SABA),
- short-acting muscarinic antagonist (SAMA) (in single, dual or triple therapy)
- Other respiratory pharmacological therapies (theophylline)
- None (no prior baseline pharmacological therapy).

To identify possible drivers of treatment choice, analyses will be conducted in subgroups according to:

- Year of initial COPD diagnosis
- Comorbid asthma diagnosis
- Lung function grade (GOLD stage 1, 2, 3 or 4 [2])
- mMRC dyspnea scale score
- Baseline exacerbation rate.

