3.0 Study population

3.1 Inclusion and exclusion criteria

Inclusion criteria

COPD diagnosis with QoF approved read codes

Age \geq 40 years

Patients have one year of practice data prior COPD diagnosis and 2 years of practice data after COPD diagnosis

Spirometry data supportive of a COPD dx in the 5 year window around date of diagnosis.

Patients must be diagnosed within the last 15years

Exclusion criteria

Patients aged less than 40 at diagnosis

No valid spirometry data available

Patients diagnosed earlier than 1997

Table 1: Inclusion and exclusion criteria

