3.2 Data source

The study will use patient data from the Optimum Patient Care Research Database (OPCRD). The study team work with fully anonymised data, removed of any patient identifiable information. The OPCRD is developed, maintained and owned by Optimum Patient Care, a social enterprise company that aims to improve patient outcomes through medical research and services. OPC provides evidence based recommendations to UK general practices through bespoke software and practice reports.

The OPCRD currently comprises longitudinal medical records for over 2.2 million patients from over 550 primary care practices across the UK. The OPCRD contains two types of data:

- routinely recorded clinical data and
- questionnaire responses from over 40,000 respiratory patients.

The OPC questionnaires are a compilation of validated questions covering symptoms, disease control, triggers, side effects, quality of life and unique adherence measures. Indeed the OPCR is the only database in the UK which compliments routinely recorded disease coding and prescribing information with patient reported outcomes. OPCR also links with nationwide practice prescribing data to enable targeted delivery of dataset needs.

The database has received a favourable opinion from the Health Research Authority for clinical research use (REC reference: 15/EM/0150). It is governed by The Anonymous Data Ethics Protocols and Transparency (ADEPT) committee, an independent body of experts and regulators commissioned by the Respiratory Effectiveness Group (REG) to govern the standard of research conducted on internationally renowned databases. All research using OPCR will be registered on recognised study databases such as the European Network of Centres for Pharmacoepidemiology and Pharmacovigilance (ENCePP).

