5.4 Analysis of study outcomes

COPD initial treatment patterns

Logistic regression analysis for all patients receiving first COPD therapy. This analysis will be conducted on:

- a. All patients receiving first COPD therapy
- b. The subgroup of patients who receive their first therapy on their date of COPD diagnosis

This will be carried out as follows:

Investigate the COPD therapy distribution of by the following main potential predictors:

- a. Year of initial COPD diagnosis (1997-2001; 2002-2006; 2007-2010)
- b. Presence of co-morbid asthma diagnosis
- c. Lung function grade (please note that GOLD stage 2 will be used as the reference). This will also be repeated for the earlier analysis investigating predictors of initial therapy choice for all patients receiving first COPD therapy
- d. mMRC score
- e. Annual exacerbation rates
- f. GOLD group with the following comparisons:
 - B vs A
 - D vs C
 - A+B vs C+D

For each potential predictor consider:

- the distribution of initial COPD therapy (number and percentage of patients and bar chart) will be summarised
- Need to test to see if it varies among the categories of each potential predictor with a chi-square.

Predictors of initial COPD treatment

Evaluate how the potential predictors outlined above could affect the choice of initial COPD therapy in terms of:

a. Odds of being prescribed any initial COPD therapy vs. no therapy

For each potential predictor:

- The distribution of initial COPD therapy (yes/no) (number and percentage of patients and bar chart) will be summarised and a test to see if it varies among the categories of each potential predictor with a chi-square will be completed.
- Odds ratios (ORs) with their 95% confidence intervals (CIs) will be calculated using an univariable logistic regression model and a multivariable logistic regression model with stepwise reduction to derive best-fitting model of non-collinear predictors
- Presence of co-morbid asthma diagnosis used both as adjustment and as stratification variable (two multivariable models)
- Collinearity analysis on all potential predictors and confounders

b. Odds of receiving initial COPD maintenance therapy vs. short-acting agents/no therapy

For each potential predictor:

- The distribution of initial COPD maintenance therapy (yes/no) (number and percentage of patients and bar chart) will be summarised and tested to see if it varies among the categories of each potential predictor with a chi-square.

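### The planned models cannot separate a change in prescribing over time from a change in which practices supply each diagnosis cohort

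*Protocol*

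**What the plan says.** The aim in Protocol section 2.1 is stated as: "This study aims to examine the changes in prescriptions patterns over time, in order to determine the potential driving factors behind GP prescribing". Section 2.2 gives the cohorts that purpose ("Cohorts will be chosen to assess how prescription patterns have changed over time") and asks in particular whether QoF in 2004 and the licensing of tiotropium in 2002 influenced prescribing.

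Assignment is by patient: "Patients will be split into three cohorts based on their date of initial COPD diagnosis". So is the data requirement in section 3.1: "Patients have one year of practice data prior COPD diagnosis and 2 years of practice data after COPD diagnosis". Neither section asks that a practice supply patients to more than one period. Section 3.2 gives only a present-day count of practices: "The OPCRD currently comprises longitudinal medical records for over 2.2 million patients from over 550 primary care practices across the UK".

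In section 5.4, diagnosis period is the first of the main predictors, in three bands. For each predictor, odds ratios are to be "calculated using an univariable logistic regression model and a multivariable logistic regression model with stepwise reduction to derive best-fitting model of non-collinear predictors". Comorbid asthma is the only stratification variable named. The variable table in Appendix 1 is captioned as the full list, and every entry describes the patient. None describes the practice.

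**The concern.** The period OR is to be read as prescribers changing what they do. A practice whose usable records begin after 2001 can add patients only to later cohorts, while the 1997-2001 cohort can come only from practices whose records reach back that far. If the two kinds of practice prescribe differently, the pooled OR contains two parts: change within practices, and a change in which practices are observed. Adjusting for asthma, lung function, mMRC and exacerbations can take out some difference in case mix, but not a difference in prescribing habit.

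This affects the point estimate, so it is separate from the question of interval width. A cluster-robust variance corrects the interval and leaves the estimate where it was. At stake is the over-time conclusion: a shift in practice mix could create, hide or reverse a period effect that would then be credited to QoF or to the tiotropium licence.

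**Working it through.** The protocol gives no sample size, power or expected period OR, so there is no figure to reproduce. It also gives no record start dates, no practice counts by period and no prescribing rates by practice. All rates, shares and sample sizes below are assumptions that show how the mechanism works.

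**1. Later-starting practices join; no practice changes its prescribing**

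Inputs (assumed): long-record practices treat 85%; later-starting practices treat 85% minus d; they supply a share s of the last cohort and none of the first.

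- Treated share in the last cohort = (1 − s) × 0.85 + s × (0.85 − d)
- Spurious OR = odds(last cohort) / odds(0.85), with odds(0.85) = 0.85/0.15 = 5.667

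Example, d = 0.10 and s = 0.4: 0.6 × 0.85 + 0.4 × 0.75 = 0.81; odds 0.81/0.19 = 4.263; OR = 4.263/5.667 = 0.75.

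| Later-starting practices | s = 0.2 | s = 0.4 | s = 0.6 |
|---|---|---|---|
| 5 points lower | 0.93 | 0.86 | 0.80 |
| 10 points lower | 0.86 | 0.75 | 0.66 |
| 5 points higher | 1.08 | 1.18 | 1.29 |
| 10 points higher | 1.18 | 1.43 | 1.78 |

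The last two rows use the same formula with the sign of d reversed. For example, 10 points higher with s = 0.6 gives 0.4 × 0.85 + 0.6 × 0.95 = 0.91; odds 0.91/0.09 = 10.11; OR = 10.11/5.667 = 1.78.

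**2. Two practice types present in both periods; only their shares move**

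The true within-practice OR is 1. Power is for a two-sided test at 0.05 with an assumed 2000 patients per period.

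| Prescribing, low / high type | Share of high type | Overall treated | Crude OR | OR stratified by practice type (Mantel-Haenszel) | Chance of p < 0.05 |
|---|---|---|---|---|---|
| 60% / 70% | 50% to 60% | 65% to 66% | 1.05 | 1.00 | 10% |
| 55% / 75% | 40% to 60% | 63% to 67% | 1.19 | 1.00 | 76% |
| 60% / 75% | 30% to 70% | 64.5% to 70.5% | 1.32 | 1.00 | 98% |
| 50% / 80% | 20% to 80% | 56% to 74% | 2.24 | 1.00 | about 100% |

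With a constant mix the crude OR is 1.00 in every case. The artefact depends wholly on how far the mix moves and how far the practice types differ.

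**3. A real change can be hidden**

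Take 60% and 75% with a true within-practice OR of 1.30. The later rates become 1.95/2.95 = 66.1% and 3.9/4.9 = 79.6%. If the share of the higher-prescribing type falls from 70% to 30%, the overall rate goes from 0.7 × 75% + 0.3 × 60% = 70.5% to 0.3 × 79.6% + 0.7 × 66.1% = 70.15%. The crude OR is 0.98.

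**4. Conditional and marginal ORs differ without any bias**

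In the same setting with a constant 50:50 mix, the crude OR is 1.29 against a within-practice OR of 1.30. The gap is small here, but the two estimates should not be expected to match exactly.

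**The case against.** A reader might infer that the early and late cohorts do come from different practices, so that the period OR is known to be wrong. The documents do not support that. Section 3.2 describes longitudinal records from the practices now in the database, which is compatible with each practice supplying its history for all three periods. The bias needs both a shift in mix and a link between record start and prescribing level, and the protocol shows neither. Nor does it give any reason to expect later-starting practices to treat less, so no direction can be claimed. This part of the objection stands in full.

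It can also be said that handling of practice is ordinary SAP content, and that a variable list need not include a stratum identifier. That has some weight, since the SAP was not available. But section 5.4 already states the model, the predictors and the only stratifier, and section 2.2 states how the period contrast will be interpreted. A better method for that stated aim is a fair point against the protocol.

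A third objection is that an all-practice contrast legitimately answers how prescribing patterns changed. It does, as a description, so it should be kept. It cannot by itself support a statement about prescribers' behaviour, which is the use that sections 2.1 and 2.2 make of it.

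Finally, period is one predictor among six, and the mock regression table (Table 4, Appendix 3) has no row for it. But that table is labelled an example, section 5.4 plans ORs for every listed predictor, and period is the first row of mock Table 3.

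**Conclusion.** The concern holds as an uncontrolled possible bias, not as a demonstrated error. Cohort entry is by patient, nothing in the protocol keeps the set of practices constant across periods, and the stated models cannot separate change within practices from differences between them. Clustered standard errors alone would not repair this.

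Size and direction are unknown. Under the assumptions in the first table, the spurious OR runs from 0.66 to 0.93 if later-starting practices treat less and from 1.08 to 1.78 if they treat more. Under a constant mix it is 1.00. For scale, the lung-grade ORs in the protocol's own example table lie between 0.87 and 1.13, so an artefact of moderate size could pass for a finding.

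The change is worth making because it is cheap and serves a stated aim. The point does not reach the ORs for asthma, lung function, mMRC or exacerbations, and it does not make the all-practice estimate invalid as a description.

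**What to change.** 1. Carry an anonymised practice identifier in the extract, and report the number of contributing practices and eligible patients for each cohort. This shows at once whether the mix shifted.
2. Keep the all-practice period OR. Beside it, report a within-practice period OR from conditional logistic regression stratified by practice, with the same patient-level predictors.
3. Use every practice with patients in at least two cohorts. Restriction to practices present in all three is unnecessary, because a practice with two cohorts still informs that comparison. Avoid unconditional practice dummies where practices are small, since they can bias odds ratios.
4. State in section 5.4 that a period difference will be attributed to changed prescribing behaviour only if the within-practice estimate supports it, allowing for the ordinary gap between conditional and marginal odds ratios. Even then, the estimate does not by itself identify QoF or the tiotropium licence as the cause.

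Cost: one identifier, one table and one more model. Practices with patients in only one cohort, or with no variation in the outcome, do not inform this contrast, so its confidence interval widens. The other predictors' planned analyses are unaffected.

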12.0 APPENDIX

12.1 Appendix 1: Definitions

Variable Name	Description	Time Period
Year of COPD diagnosis	Year of First COPD diagnosis	n/a
IDD Cohort	Year of first COPD diagnosis split into three cohorts: 1997 -2001, 2002 - 2006, 2007 - 2010	n/a
Age	Age at COPD diagnosis	n/a
Gender	Gender of patient: Male, Female	n/a
Smoking Status	Smoking status recorded in routine medical notes closest to date of COPD diagnosis	Closest to date of COPD diagnosis
Body Mass Index (BMI)	BMI defined as: Underweight = < 18.499, Normal = $\geq 18.50 - 24.99$, Overweight = ≥ 25.00 , Obese = ≥ 30.00	Closest to date of COPD diagnosis
Exacerbation Rate	Exacerbations were defined as: (i) COPD-related hospital admissions or Emergency Department attendance; (ii) use of acute oral steroids; (iii) General practitioner consultations for lower respiratory tract infections. Two exacerbations occurring within 2 weeks of one another were counted only once.	Calculated during the year prior to and including the date of COPD diagnosis.
mMRC Score	mMRC scores were based on the 5-point 162 scale of the British Medical Research Council questionnaire assessing perceived breathlessness. Combined mMRC score from either routine medical notes or questionnaire data if available.	Closest to date of COPD diagnosis
Lung Function Group	Lung function grade was calculated using GOLD Stage 1, 2, 3 and 4 criteria	Closest to date of COPD diagnosis
Asthma Diagnosis	Presence / absence of a co-morbid diagnosis of Asthma in routine medical notes	Closest to date of COPD diagnosis
Rhinitis Diagnosis	Presence / absence of a co-morbid diagnosis of Rhinitis in routine medical notes	Closest to date of COPD diagnosis
Gastroesophageal reflux disease (GERD)	Presence / absence of a co-morbid diagnosis of GERD in routine medical notes	Closest to date of COPD diagnosis
Heart Failure	Presence / absence of a co-morbid diagnosis of Heart Failure in routine medical notes	Closest to date of COPD diagnosis
Chronic Kidney Disease	Presence / absence of a co-morbid diagnosis of Chronic Kidney Disease in routine medical notes	Closest to date of COPD diagnosis
Osteoporosis	Presence / absence of a co-morbid diagnosis of Osteoporosis in routine medical notes	Closest to date of COPD diagnosis

Diabetes	Presence / absence of a co-morbid diagnosis of Diabetes in routine medical notes	Closest to date of COPD diagnosis

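### The tiotropium licence and QoF both fall inside the 2002-2006 cohort, so the three-period factor cannot attribute a change in either modelled outcome to one of them

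*Protocol*

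**What the plan says.** Section 2.2 gives the reason for the cohorts: "Cohorts will be chosen to assess how prescription patterns have changed over time and if certain factors such as", continuing with the two events it names, "the introduction of QoF1 in 2004 and Tiotropium (LAMA) becoming licensed in UK in January 2002 influence prescribing behaviour". Patients are then divided by date of first diagnosis into 1997-2001, 2002-2006 and 2007-2010.

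The same three levels recur throughout. Section 5.4 lists them as the first potential predictor, Appendix 1 defines the cohort variable as "Year of first COPD diagnosis split into three cohorts: 1997 -2001, 2002 - 2006, 2007 - 2010", and mock Tables 2 and 3 use them. Appendix 1 also lists the single calendar year, "Year of First COPD diagnosis", but section 5.4 does not enter it in that form.

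The modelled outcomes are any initial therapy versus none, and maintenance therapy versus short-acting agents or none. Each is analysed by univariable and stepwise multivariable logistic regression. Initial therapy is "pharmacological therapy prescribed during one year prior to and at the initial date of COPD diagnosis". The synopsis states the objective as to "highlight predictors over time in GP prescription of" these two outcomes.

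**The concern.** The grouping does not match the purpose given for it. Of the two events named, only the licence sits on a cohort boundary. QoF falls inside the middle cohort, and the other cut, at 2007, matches no event that the protocol names.

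The risk is misattribution. Because the first cut coincides with the licence, a difference between the first two cohorts will naturally be credited to tiotropium, although most of the middle cohort may have been diagnosed under QoF. A QoF effect would meanwhile be divided between two contrasts and look smaller in each. This is a rule that the protocol fixes, not a detail it leaves open.

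**Working it through.** The protocol gives no sample size, power or effect size for this point, so there is no figure of its own to reproduce. The check sets the event dates against the cohort boundaries.

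**Inputs from the protocol.** Licence January 2002; QoF 2004, month not given; cohorts 1997-2001, 2002-2006 and 2007-2010; one-year look-back for initial therapy.

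**Assumptions.** Equal numbers of diagnoses per year; immediate step effects on the log-odds scale; log-odds averaged within a cohort. All of 2004 counts as post-QoF unless stated.

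**Step 1: exposure by cohort.** Let T be the log odds ratio for the licence and Q that for QoF.

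| Cohort | Share post-licence | Share post-QoF |
|---|---|---|
| 1997-2001 | 0 | 0 |
| 2002-2006 | 1 | 3/5 = 0.6 |
| 2007-2010 | 1 | 1 |

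If QoF began at the very end of 2004, the middle share is 2/5 = 0.4, so the range is 0.4 to 0.6.

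**Step 2: what the contrasts estimate.** The mean diagnosis years are 1999, 2004 and 2008.5. With a linear trend b per year:

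- 2002-2006 vs 1997-2001 = T + 0.6Q + 5b
- 2007-2010 vs 2002-2006 = 0.4Q + 4.5b

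There are two equations and three unknowns. A model with a constant, both steps and a trend has rank 3 of 4 on the planned cohorts. On the 14 single years 1997-2010 it has rank 4 of 4.

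**Step 3: a QoF effect alone (T = 0, b = 0).**

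| QoF OR | 2002-2006 vs 1997-2001 | 2007-2010 vs 2002-2006 |
|---|---|---|
| 1.5 | exp(0.6 × 0.4055) = 1.275 | exp(0.4 × 0.4055) = 1.176 |
| 2.0 | exp(0.6 × 0.6931) = 1.516 | exp(0.4 × 0.6931) = 1.320 |

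The log-odds averaging matters little. With 50% prescribing before QoF, an OR of 1.5 gives 60% afterwards. The middle cohort then has 0.4 × 50% + 0.6 × 60% = 56%, odds 0.56/0.44 = 1.27, and the second contrast is 1.5/1.27 = 1.18.

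**Step 4: different causes, same cohort results.** Each row gives log odds of 0.6 and 0.2 for the two contrasts, that is ORs of 1.82 and 1.22. The effects are illustrative.

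| T (OR) | Q (OR) | b | T + 0.6Q + 5b | 0.4Q + 4.5b |
|---|---|---|---|---|
| 0.300 (1.35) | 0.500 (1.65) | 0 | 0.6 | 0.2 |
| 0.370 (1.45) | 0.050 (1.05) | 0.04 | 0.6 | 0.2 |
| 0.405 (1.50) | -0.175 (0.84) | 0.06 | 0.6 | 0.2 |

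The planned factor cannot distinguish a positive QoF effect from none or from a negative one.

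**Step 5: look-back.** For diagnoses spread evenly over 2002, on average half of the look-back year precedes the licence; for 2003 diagnoses, none does. That is 0.5/5 = 10% of the planned middle cohort's look-back time, and 0.5/2 = 25% of a 2002-2003 group's.

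**The case against.** The protocol does not promise a separate effect estimate for each event. They appear once, as examples of factors, and not among the objectives or outcomes. This stands and limits the point, but they are still the reason given for the cohorts.

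The two effects could be solved from the two contrasts. That requires immediate steps, a known pre/post-QoF mix and no other trend. The protocol states none of these and sets out to study change over time.

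Tiotropium uptake can be seen elsewhere. This is partly right: LAMA is its own therapy class in section 2.2, and section 5.4 tabulates therapy by diagnosis period. The two modelled outcomes, however, do not separate LAMA, and nothing comparable exists for QoF.

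The illustrative odds ratios are hypothetical. They are, and in the same scenario 2007-2010 versus 1997-2001 recovers the full 1.5 or 2.0. That contrast estimates T + Q together, which does not help to separate them.

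A SAP, not shown, might analyse single year of diagnosis, which Appendix 1 holds. Nothing forbids it, but the protocol itself fixes three levels in its analysis section.

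A reader might go further on three points, and the protocol supports none of them:

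- **That the study cannot answer its time question.** Three successive cohorts do describe change over time.
- **That changing predictors cannot be shown.** Section 2.2 plans subgroup analyses by year of diagnosis, and section 5.4 does not exclude interactions.
- **That period is left out of the models because mock Table 4 has no row for it.** That table is captioned as an example and also lacks GOLD group, another listed predictor. Table 3 does show year of diagnosis.

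**Conclusion.** The point holds in a limited form. With no cut at 2004, neither planned contrast between adjacent cohorts isolates the licence or QoF once a calendar trend is allowed, and a change in either modelled outcome cannot be attributed to one event.

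That conclusion follows from the dates alone. The size does not: the 1.275 and 1.18 for a true QoF OR of 1.5 rest on equal diagnoses per year, all of 2004 as post-QoF, no tiotropium effect and no trend. If QoF began at the end of 2004, the two figures change places.

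Description of change over time, descriptive LAMA uptake by cohort, and the analyses of the other predictors are not undermined. The change is worth making before analysis because it is cheap and concerns a purpose that the protocol states.

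**What to change.** Choose one of the following:

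1. **Four periods:** 1997-2001, 2002-2003, 2004-2006 and 2007-2010. Mean years are 1999, 2002.5, 2005 and 2008.5, so adjacent contrasts become T + 3.5b, Q + 2.5b and 3.5b. Both events can then be estimated under a linear trend, but with four cells and four parameters nothing is left to test linearity.
2. **Single calendar year** with a trend and step terms at January 2002 and at QoF introduction. The protocol should state the QoF start date.

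In either case, keep the time term in the multivariable models so that stepwise reduction cannot remove it.

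If the three cohorts are kept, state that their contrasts describe change over time and cannot be attributed to QoF or tiotropium individually.

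**Cost.** Year of first diagnosis is already held, so no new data are needed for the four periods. The 2002-2003 group covers two years and will have wider intervals. The one-year look-back blurs both cuts: about 25% of that group's look-back time precedes the licence, and 2004 diagnoses look back into 2003. A sensitivity analysis excluding diagnoses in the first year after each event is advisable, although it leaves only 2003 in that group.
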